## **2. STUDY OBJECTIVES**

### **2.1. Primary Clinical Efficacy Objective**

To assess the efficacy of Aerucin®, administered as a single dose in addition to standard of care (SOC) antibiotic regimen on Clinical Cure rates (resolution of pneumonia) between SOC alone and SOC with Aerucin® at Day 21.

### **2.2. Primary Clinical Safety Objective**

To assess the clinical safety and tolerability of Aerucin® in the study population.

### **2.3. Secondary Clinical Efficacy Objectives**

To assess the effect of Aerucin®, administered as a single dose in combination with SOC antibiotic regimen as an adjunct therapy of *P. aeruginosa* pneumonia, as compared to standard antibiotic therapy alone, on the following parameters:

1. Clinical Cure rates at Day 28, 14 and 7, using the same criteria as for the primary efficacy objective.
2. Time to Clinical Cure.
3. Mortality and Pneumonia-related mortality post-treatment.
4. Respiratory functional assessment: Time on mechanical ventilation (including if tracheostomy is in place). Time on supplemental oxygenation. Measures of respiratory health such as changes in PaO2/FiO2, using arterial blood gases and/or pulse oximetry measurements.
5. Overall clinical status: Changes in sequential organ failure assessment (SOFA) score.
6. Health economics: antibiotic utilization, duration of stay in the intensive care unit (ICU), duration of hospitalization, duration of intubation with ventilation or duration of mechanical ventilation if tracheostomy in place.

### **2.4. Pharmacokinetics (PK) Objective**

To assess the PK Profile of Aerucin®.

### **2.5. Secondary Safety Objectives**

To assess the immunogenicity of Aerucin®.

## 2.6. Microbiological Efficacy Objectives

To assess the effect of Aerucin®, administered as a single dose in combination with SOC antibiotic regimen as an adjunct therapy of *P. aeruginosa* pneumonia, as compared to standard antibiotic therapy alone, on the following parameters:

1. Eradication of index *P. aeruginosa* at Day 21 and 28 post-treatment,
2. Re-infection/new infection defined as a reoccurrence of pneumonia due to *P. aeruginosa* within the 28-day follow-up period,
3. Reduction in bacterial load related to the index *P. aeruginosa*

## 3. STUDY DESIGN

### 3.1. General Study Design and Plan

This study is an international, multicenter, prospective, double blind, randomized, placebo-controlled, parallel design protocol. It will be performed at multiple ICUs.

Patients with a documented diagnosis of pneumonia, due to *P. aeruginosa*, and require ICU care, who are intubated (or have a tracheostomy tube in place) and are mechanically ventilated, are eligible for screening.

Patients meeting all other eligibility requirements will be assessed for *P. aeruginosa* pulmonary infection on the basis of culture results (known from recent quantitative/semi-quantitative cultures) or on the basis of rapid diagnostic testing of a fresh airway specimen using methods available at the site (e.g. mass spectrometry, Polymerase Chain Reaction, etc.), or using devices such as CE marked Cepheid's GeneXpert® with "Investigational / Research Use Only" (IUO / RUO) PA Cartridge, or BioFire Diagnostics, LLC (a BioMerieux company)'s IUO FilmArray® LRTI Panel.

Acceptable airway samples are broncho-alveolar lavage (BAL), mini-BAL, or endotracheal aspiration (ETA) (ETA sample with <10 squamous epithelial cells and >25 polymorphonuclear cells per low power field). It is expected that some subjects will have a positive rapid diagnostic test result that will not be confirmed by standard microbial culture (quantitative, or semi-quantitative). These subjects will be followed according to all the procedures described in this protocol but will not accrue toward the target microbiologically evaluable intent to treat population (micro-ITT). Subjects with a positive diagnosis of *P. aeruginosa* pulmonary infection will be randomized to receive either investigational product or matching placebo (more than one pathogen allowed, if *P. aeruginosa* is regarded a key pneumonia causing pathogen). In total, approximately 154 microbiologically evaluable subjects will be randomized 1-1 to be treated with placebo plus SOC or Aerucin® (20 mg/kg) plus SOC in this Phase 2/3 study.

The randomization procedure will account for the fact that many study sites will enroll only a few patients. Randomization will account for existence of sub-populations regarding oxygen status at baseline (PaO2/FiO2 ≤200 or >200).

Study subjects will receive a single treatment dose (at Day 0) in addition to SOC antibiotic treatment, and then enter a safety, efficacy and PK follow-up study period for a total study duration of 28 days. The selection of SOC antibiotics is made in accordance with local best practices at the discretion of the investigator and should not exceed a duration of 14 days.

The clinical course of pneumonia will be assessed daily by the investigator. Once Clinical Cure has been determined, the clinical status of the subject will be monitored to confirm continuation of Clinical Cure, re-infection (pneumonia due to *P. aeruginosa*), or new infection (pneumonia due to an unknown pathogen or a pathogen other than *P. aeruginosa*). “Clinical Cure” can be declared at any time during the study by the PI provided, that the required criteria are met either based on documented improvements in signs and symptoms, +/- changes documented by chest X-ray (if performed as part of SOC), as interpreted by the investigator.

The assessment of Clinical Cure (resolution of pneumonia) by the site investigator will be used for the primary analysis. An adjudication committee will apply newly defined Clinical Cure criteria post hoc in a secondary analysis. “Clinical Cure” will be assessed for analytical purposes on Day 7, 14, 21 (primary efficacy endpoint) and 28.

Clinical safety assessments will be performed on an ongoing basis while predefined laboratory assessments will be performed at baseline, and thereafter at Day 4, 7, 14, 21, and 28. Test results obtained for medical reasons between these mandatory time points will be assessed for adverse events and documented accordingly.

Secondary efficacy endpoints will be assessed in a similar manner during the 28-day period, when appropriate, daily when possible (e.g., time on mechanical ventilation including if tracheostomy is in place, time on supplemental oxygenation, measures of respiratory health such as changes in PaO2/FiO2 using arterial blood gases and/or pulse oximetry measurements), or upon occurrence (e.g., antibiotic utilization, duration of stay in the ICU, duration of hospitalization, duration of intubation with ventilation, or duration of mechanical ventilation if tracheostomy in place).

Microbiological endpoints of eradication and re-infection/new infection will be determined based on quantitative/semi quantitative cultures performed by the local laboratory and testing of isolates performed by a central microbiology laboratory.

Two PK analyses will be performed to assess the PK profile of Aerucin® in the target patient population. The pharmacokinetics of Aerucin® will be assessed using a population PK (compartmental modeling) approach as well as a non-compartmental analysis approach. A PK sub-study (“Full PK”) will be included, wherein more extensive sampling will be performed in a small number of patients (from select sites) who provide consent (i.e., 16 patients to obtain 8 patients on active treatment). In the remaining patients, a sparse sampling strategy will be implemented with only a few samples obtained from each patient at varying time points (“Sparse PK”). A compartmental population PK model will be developed using the PK data collected from the sub-study and the sparse samples. PK parameters will be estimated as well as between-subject or inter-individual variability and residual variability. The effects of select factors describing the characteristics of sub-populations of interest (e.g. high or low bacterial load, cause of admission [trauma or non-trauma], and type of pneumonia) on the PK of Aerucin® will be assessed via covariate analysis. In addition to the population PK evaluation, non-compartmental analysis of the PK sub-study data will be performed.

The investigational therapy will be studied as an adjunct to antibiotic therapy as prescribed by the study investigator according to the SOC in his/her institution. The duration and nature of the initial and any subsequent antibiotic therapy related to the baseline pneumonia event and other infections will be recorded. Duration of antibiotic treatment for the index pneumonia should not exceed 14 days.

### **3.2. Randomization and Blinding**

This is a double-blind, placebo-controlled study. Study subjects will be first stratified as follows:

- Stratum 1: ventilator-associated bacterial pneumonia (VABP) or non-VABP
- Stratum 2: PaO2/FiO2 ≤200 or >200
- Stratum 3: Americas, Eastern EU, Western EU and Asia

Randomization will proceed in a 1:1 ratio, in blocks of 4, for the study overall.

A computer-generated randomization schedule will be used to allocate study treatment according to the above randomization scheme. Upon confirmation of eligibility, the study personnel will be prompted to randomize the study subject using the electronic data capture (EDC) / interactive web-based randomization system (IWRS) system.

### **3.3. Breaking the Blind**

The Investigator will be allowed to break the blind if, in his/her opinion, this is necessary to provide proper medical care to his/her patient. In general, study drug unblinding should not impact any necessary treatment decisions by the investigator. Prior to breaking the blind, the Investigator will confer with the Medical Monitor to confirm the necessity of such action.

In the absence of the Investigator, the Medical Monitor may break the blind for a specific study subject under such urgent circumstances and after assessing the necessity of such action with a sub-investigator.

Members of the Data Monitoring Committee (DMC) will be allowed to break the blind if it is deemed necessary to assess specific adverse events.

The circumstances leading to breaking the blind will be fully documented in detail in a memo to file and as required, in the EDC system.

### **3.4. Study Drug Administration**

Upon randomization, the number of vials of study drug based on subject's weight required for treatment will be displayed by the EDC / IWRS system, and access will be given to the inventory corresponding to the treatment allocation of the subject. Study personnel will then select the specific vials required, up to a maximum of 20 vials from the inventory available on site. Subjects weighing over 120 kg will receive the amount of Aerucin® or placebo corresponding to 120 kg, i.e. 20 vials.

The entire content of the bag must then be administered intravenously at room temperature in approximately 2 hours. The study drug will be administered once, intravenously, in a strictly monitored setting.

### **3.5. Study Assessments**

Table 1 presents the schedule of assessments of the study.

**Table 1. Schedule of Assessments**

Visit	Screening, Baseline, and Randomization	Treatment	Follow-up (Daily until index pneumonia is considered resolved)	Follow-up Any setting	End of Study  or Early Termination 
Day	-1	0	1 to 28 Daily	4, 7, 14, 21	28 or Day of Termination
Informed Consent	X				
Eligibility	X				
Demographics	X				
Type of Pneumonia 	X				
Medical history	X				
Surgical History	X				
Case history	X				
Concomitant medications	X	X	X	X	X
Physical exam	X			X	X
Vital signs 	X	X	X	X	X
12-lead ECG	X				
Safety laboratory tests	X		X 	X	X
Sampling: ADA	X 				X
Sampling: Future Biomarkers (where applicable)				X	X
Sampling: PK	X 	X 	X 	X 	X 
Microbiology: rapid testing	X				
Microbiology: classic	X		X 	X 	X 
Sampling: microbiology	X		X 	X 	X 
Respiratory data	X	X 	X 	X	X
Arterial gases or pulse oximetry 	X	X		X	X
PaO 2 /FiO 2 ratio	X	X	X	X	X
APACHE II	X				
SOFA	X	X	X 		
Randomization	X 				
Treatment		X			
Assessment of Clinical Cure			X 	X	X
Adverse events		X	X	X	X
Chest X-Rays	X 				
Pregnancy Test (Urine or Serum)	X 				
Discharge data					X 
Study Follow-Up Phone Call				X 	X 

Visit	Screening, Baseline, and Randomization	Treatment	Follow-up (Daily until index pneumonia is considered resolved)	Follow-up Any setting	End of Study  or Early Termination 
Day	-1	0	1 to 28 Daily	4, 7, 14, 21	28 or Day of Termination

 
1. To be performed if medically necessary. Follow-up airway specimens to be obtained as medically necessary and prior to extubation and at Day 28 (if not extubated prior to then) for quantitative or semi-quantitative culture.
 
2. SOFA and respiratory data to be collected on Day 0, 12 hours after treatment initiation and on Day 4, 7, 14, 21, 28 while intubated and mechanically ventilated. Parameters for SOFA score calculation should not be older than 72 hours.
 
3. ADA only at screening / baseline and Day 28, or at early termination.
 
4. Pre-dose PK sample to be obtained prior to treatment initiation.
 
5. PK samples to be obtained for the FULL PK sub-study at the following times after initiation of treatment: 2 hours (end of infusion), 4h, 12h, and 24 hours and 1 sample at each of the following visits: Day 4, 7, 14, 21, and 28.
 
6. PK samples for the SPARSE PK sub-study at the following times after initiation of treatment: 1 sample at 2 hours (end of infusion), 1 sample at either 4h, 12h, or 24 hours post-treatment initiation (inclusive) and 1 sample at any of the following visits: Day 4, 7, 14, 21, or 28.
 
7. Eligible subjects are randomized on Day -1, Treatment day is Day 0 for the purpose of monitoring and collecting the required samples over the first 24 hours.
 
8. Clinical Cure will be assessed at Day 7, 14, 21, 28 for the analytical purposes.
 
9. Discharge data to be obtained when discharge occurs or Day 28, whichever occurs first.
 
10. Patients with pneumonia who are intubated are eligible for screening regardless of the type of pneumonia, which will be recorded at the time of screening for all study subjects.
 
11. Vital signs will be recorded at baseline prior to treatment (time 0) and then at 1, 2, 4, 12, and 24 hours post treatment. Vital signs will also be recorded daily thereafter.
 
12. In addition to the screening timepoint, chest x-ray(s) are to be taken at any time as medically indicated.
 
13. Women of child bearing potential must take a urine or serum pregnancy test at the time of Screening.
 
14. For subjects with early discharge, effort must be made to perform all protocol defined procedures outlined for End of Study/Early Termination.
 
15. Subjects who decide to discontinue study assessments prior to Day 28 will receive a study exit safety follow-up phone call on key days (Day 4, 7, 14, 21, 28) until Day 28 (+7 days) to assess Clinical Cure, survival and the status of any adverse events.
 
16. Changes in PaO2/FiO2 ratio (e.g. by arterial blood gases), if available and whenever possible OR changes in non-invasive measures of oxygenation (e.g. by pulse oximetry)
 
17. A few days before or after the specified date is acceptable (<math>\pm 2</math> days)
 
					

#### 4. SAMPLE SIZE DETERMINATION

The primary efficacy endpoint is the proportion of subjects with Clinical Cure at Day 21.

It is assumed that the proportion of subjects with Clinical Cure will be 65% in the placebo group, and 85% in the 20 mg/kg dose group. With 69 subjects per group, there will be >90% power for a statistically significant difference at a two-sided 0.05 level of significance. Sample size calculation was performed based on Fisher's Exact test using binomial enumerations (PASS version 14). Assuming a 10% drop-out rate, approximately 154 subjects (77 per group) will be randomized.

#### 5. STUDY ENDPOINTS

##### 5.1. Primary Clinical Efficacy Endpoint

The primary efficacy endpoint is the proportion of patients with Clinical Cure at Day 21 in patients treated with Aerucin® versus the placebo group as assessed by the investigator. The investigators' assessment will be the primary analysis of the primary endpoint.

Additionally, newly defined Clinical Cure criteria (Table 2) will be applied post-hoc by an independent adjudication committee.

**Table 2**                    **Criteria for Clinical Cure**

---

1.	The subject must be alive through the index day visit
----	---

---

2.	The patient must have improved respiratory function evaluated at the index day, because: 

• The patient is now off the ventilator and extubated

	or
3.	if the patient entered the study with mechanical ventilation due to reasons other than pneumonia and was assessed " likely ventilated beyond day 28 " at screening, criteria #1 (survival) and #4 (no signs and symptoms of pneumonia) are sufficient to establish Clinical Cure ( presumed not ventilated )

---

4.	The subject must show no clinical signs and symptoms of bacterial pneumonia at the index day, which is determined by 

• Not receiving any antibiotic therapy active against the initial P. aeruginosa strain or against persisting pulmonary bacterial infection for 48 hours (antibiotic therapy for documented extra-pulmonary infection permitted)

	and
	• Resolution of signs and symptoms of bacterial pneumonia, as determined by the PI based on their clinical assessment . Parameters to be considered may include: 

○ Absence of lung abscess or empyema

○ Fever > 38°C or hypothermia (< 35°C) attributable to the primary bacterial pneumonia

○ Tachypnea or shortness of breath (> 22 respirations/min) if off the ventilator and/or back to baseline respiratory rate

---

- 
- Tachycardia (> 100 bpm) or bradycardia (< 60 bpm) and/or back to baseline heart rate
  - Improvement of hypoxemia (ABG or PaO2/FiO2 > 200 or pulse oximetry > 90%)
  - If patient still produces sputum - negative *P. aeruginosa* culture from sputum, blood or pleural fluid
- 

## 5.2. Secondary Clinical Efficacy Endpoints

The secondary clinical efficacy endpoints are the following:

1. Proportion of patients with Clinical Cure at Day 28
2. Proportion of patients with Clinical Cure at Day 14
3. Proportion of subjects who died (All-cause mortality) at Day 28
4. Proportion of subjects who died due to pneumonia (Pneumonia-related mortality) at Day 28
5. Proportion of patients with Clinical Cure at Day 7
6. Change from baseline in respiratory functional assessment: Time on mechanical ventilation (including if tracheostomy is in place). Time on supplemental oxygenation. Measures of respiratory health such as changes in PaO2/FiO2, using arterial blood gases and/or pulse oximetry measurements.
7. Mean change from baseline in overall clinical status measured by SOFA scores.
8. Health economics: antibiotic utilization, duration of stay in the ICU, duration of hospitalization, duration of intubation with ventilation or duration of mechanical ventilation if tracheostomy is in place.

## 5.3. Microbiological Endpoints

The microbiological endpoints have the following:

1. Microbiological outcome as measured by the proportion of subjects with the index *P. aeruginosa* pneumonia based on the data provided by the local microbiology laboratory and central microbiology laboratory.
2. Proportion of subjects achieving the eradication of *P. aeruginosa* at Day 21 and 28. Eradication is considered as obtained when a specimen of respiratory secretions is obtained between the visit day and Day 28 and is negative. When no specimen is obtained within this time frame, microbiological outcome will be assessed as “Eradicated” only if the study subject is not receiving any antibiotic active against the initial strain after the study drug administration visit day and displays no signs and symptoms of pneumonia.
3. Change in bacterial load related to the index *P. aeruginosa* on the basis of quantitative or semi-quantitative cultures by the local microbiological laboratory.

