9.3.5 Missing data

Assessing microbiological outcome at Day 7, 14, 21 (Primary Efficacy endpoint), and 28 will be done using the nearest microbiological data available prior to that day (last observation carried forward, LOCF).

Missing data for secondary efficacy endpoints will be analyzed using the LOCF approach.

For the purpose of sensitivity analysis, missing data will be imputed using baseline observation carried forward (BOCF) and observed case.

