#### **6.1.5. Handling of Dropouts and Missing Data**

Missing data will be handled as follows:

- For clinical outcome at Day 7, 14, 21, and 28, missing data will be handled using the nearest clinical data available prior to that day, i.e. last observation carried forward (LOCF) approach.
- For microbiological outcome at Day 7, 14, 21, and 28, missing data will be handled using the nearest microbiological data available prior to that day, i.e. **LOCF approach**.
- In cases of missing or incomplete dates [e.g. adverse event (AE) and concomitant medications], the missing component(s) will be assumed as the most conservative value possible. For example, AEs with missing start dates, but with stop dates either overlapping into the treatment period or missing, will be counted as treatment-emergent, taking the **worst-case approach**. When partial dates are present in the data, both a partial start date and/or a partial stop date will be evaluated to determine whether it can be conclusively established that the AE started prior to the start of study drug or ended prior to the start of study drug. If the above cannot be conclusively established based on the partial and/or present dates, then the AE will be considered as treatment-emergent. Actual data values will be presented in the data listings.
- A conservative approach will be taken to assess the relationship of an AE to study drug: if the relationship of an event is missing, it will be considered treatment-related. Missing severity for an AE will not be imputed.
- **Missing values for other variables will not be imputed** and only observed values will be used in data analyses and summaries.

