### 6.4.3. Microbiological Endpoints

Microbiological endpoints include the following:

- Eradication of index *P. aeruginosa* at Day 21 and 28;
- Re-infection/new infection defined as a reoccurrence of pneumonia due to *P. aeruginosa* within the 28-day follow-up period; and
- Change in bacterial load related to the index *P. aeruginosa* on the basis of quantitative or semi-quantitative cultures by the local microbiological laboratory.

Microbiological endpoints of eradication and re-infection/new infection will be determined based on quantitative/semi quantitative cultures performed by the local laboratory and testing of isolates performed by a central microbiology laboratory.

For microbiological outcome of eradication of index *P. aeruginosa*, if no specimen of respiratory secretions is obtained at the specific time point, the nearest microbiological data available prior to that day (Day 7, 14, 21, or 28) will be used, i.e. using LOCF approach. When there is no specimen obtained prior to that day, microbiological outcome will be assessed as “Eradicated” only if the study subject is not receiving any antibiotic active against the initial strain after the study drug administration and prior to that day and displays no signs and symptoms of pneumonia.

The eradication rate of index *P. aeruginosa* and reinfection rate of pneumonia due to *P. aeruginosa* will be summarized by treatment group based on the micro-ITT Population and analyzed using a stratified CMH test based on the stratification factors at randomization. The P-value from the stratified CMH test will be presented.

Change in bacterial load ( $\log_{10}\text{cfu/mL}$ ) related to the index *P. aeruginosa* based on the local microbiological laboratory will be presented by treatment group for the micro-ITT Population.

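### With no visit-day specimen, the plan gives conflicting, unranked rules for eradication at Day 21 and Day 28, and the antibiotic condition for presumed eradication is ambiguous

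*SAP*

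**What the plan says.** Three rules cover a subject who has no specimen on the visit day.

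- **Forward window.** SAP 5.3, matching the protocol synopsis and Protocol 7.3: "Eradication is considered as obtained when a specimen of respiratory secretions is obtained between the visit day and Day 28 and is negative". If that window is empty, the rule goes straight to presumed eradication, with no carry-forward step. The antibiotic condition for presumption reads: "only if the study subject is not receiving any antibiotic active against the initial strain after the study drug administration visit day". Pneumonia signs and symptoms must also be absent.
- **Backward carry-forward.** SAP 6.4.3: with no specimen at the time point, "the nearest microbiological data available prior to that day (Day 7, 14, 21, or 28) will be used". Presumption applies only if no earlier specimen exists, and its antibiotic condition is worded differently: "if the study subject is not receiving any antibiotic active against the initial strain after the study drug administration and prior to that day". Pneumonia signs and symptoms must again be absent. SAP 6.1.5 ("missing data will be handled using the nearest microbiological data available prior to that day") and Protocol 9.3.5 ("will be done using the nearest microbiological data available prior to that day") take the same approach.
- **Closest specimen.** Protocol 6.5, 6.6 and 6.7 say that the closest specimen is used when none was taken on the visit day. They do not say whether it must come before or after that day.

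SAP 6.4.3 plans a stratified CMH test of the eradication rate in the micro-ITT population.

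**The concern.** The first two rules differ in trigger (empty window against no specimen on the day), in direction, and in what happens before presumption. No text says which prevails. Two programmers who each follow the SAP could class the same subject differently, in either direction, and report different eradication rates and p-values for the first-listed microbiological objective. If the choice is left until treatment codes are known, it becomes a data-dependent choice.

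The presumption step adds a second problem. Every subject receives background antibiotics after dosing, so a condition about antibiotics since dosing behaves very differently from one about antibiotics at the assessment.

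**Working it through.** There is no stated figure to reproduce. The check applies each rule to the same histories. Assumptions: no specimen on the visit day; a positive specimen means not eradicated; baseline is not carried forward.

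**Step 1: Day 21.** E = eradicated, N = not eradicated, P = decided by the presumption condition.

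| Last post-dose specimen before Day 21 | Specimen on Days 22–28 | SAP 5.3 | SAP 6.4.3 |
|---|---|---|---|
| positive (e.g. Day 14) | negative (e.g. Day 24) | E | N |
| negative (e.g. Day 14) | positive (e.g. Day 24) | N | E |
| negative | none | P | E |
| positive | none | P | N |
| none | negative | E | P |
| none | positive | N | P |
| none | none | P | P |
| negative | negative | E | E |
| positive | positive | N | N |

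The first two rows always disagree. The next four disagree for one of the two values of P. Splitting each row by P met or not met gives 9 × 2 = 18 logical histories. Disagreements: 2 + 2 + 1 + 1 + 1 + 1 = 8, four in each direction. This treats P as the same condition in both sections, which step 4 qualifies.

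**Step 2: Day 28.** The SAP 5.3 window shrinks to Day 28 itself, so a missing specimen leads straight to P. SAP 6.4.3 still carries the last result forward first. With three possible earlier results and two values of P there are 6 histories. The rules disagree in 2: earlier negative with P not met, and earlier positive with P met.

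**Step 3: the protocol's closest-specimen rule.** If either direction is allowed, Days 14 and 24 lie 7 and 3 days from Day 21, so Day 24 is used, in line with SAP 5.3. With specimens on Days 19 and 27 the distances are 2 and 6 days, so Day 19 is used, in line with SAP 6.4.3. This rule therefore does not settle the conflict.

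**Step 4: the antibiotic condition.** Take a subject with no post-dose specimen, active background antibiotics on Days 0 to 10 (within the 14-day limit in SAP 3.1), and no signs or symptoms at Day 21.

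| Wording | Reading | Presumed eradicated at Day 21? |
|---|---|---|
| SAP 5.3 | none after the dosing day | no |
| SAP 5.3 | none after the assessment visit | yes, if none is given later |
| SAP 6.4.3 | none at any time from dosing to Day 21 (literal) | no |
| SAP 6.4.3 | not on one at the visit (present tense) | yes |

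On the literal SAP 6.4.3 reading, any subject given active therapy after dosing fails, while one given only inactive antibiotics can pass.

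**Step 5: weight of one subject.** 100/77 = 1.30 points with the planned 77 per arm, and 100/69 = 1.45 points with 69.

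**The case against.** The best defence is that SAP 5.3 defines the endpoint and SAP 6.4.3 handles missing data, so the steps chain: window, then carry-forward, then presumption. SAP 6.1.5 and Protocol 9.3.5 do lend weight to carry-forward. But the chain is written nowhere. SAP 5.3 has its own rule for an empty window, which leaves nothing missing to fill, and SAP 6.4.3 applies carry-forward even when a Day 22–28 specimen exists.

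Four stronger readings are tempting, and the documents do not support them:

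- *The positive baseline culture is carried forward, so presumption in SAP 6.4.3 is never reached.* Protocol 9.3.5 lists baseline carry-forward separately from LOCF, as a sensitivity method, and this reading would empty an explicit sentence. One line excluding baseline is enough.
- *The SAP does not say what data feed the test.* SAP 6.4.3 names local cultures and central isolate testing. The loose end is narrower: Protocol 9.5 has the committee assess microbiological outcome for statistical use, and the SAP does not say how.
- *Day 21 specimens will usually be absent by design.* Footnote 1 to Protocol Table 6-1 and to SAP Table 1 requires follow-up specimens only as medically necessary, before extubation, and at Day 28 if still intubated. Yet Protocol 6.6 lists obtaining airway specimens among the required assessments for Days 4, 7, 14 and 21. The documents are mixed.
- *The 8 of 18 histories give a misclassification rate.* They are equally weighted logical patterns, not patients.

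**Conclusion.** The conflict stands. With no visit-day specimen, SAP 5.3 and SAP 6.4.3 can give opposite answers for one subject. The protocol carries both rules and adds a third, and nothing ranks them. The antibiotic wording of the presumption step is ambiguous in both SAP sections, in different ways.

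The number of subjects affected cannot be computed, because the documents give no specimen frequencies. A reader might infer a threat to the main result. There is none: the primary endpoint is investigator-assessed clinical cure, and eradication is not in the ordered list in SAP 6.4.2. What depends on the section followed is the reported eradication rate and its CMH p-value. That is worth correcting, though it does not bear on the trial's main claim.

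**What to change.** Before unblinding, put one ordered rule in SAP 5.3, 6.1.5 and 6.4.3. For Day X:

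1. Use the Day X specimen, with a stated visit window. (Footnote 17 to the schedules allows ±2 days for the End of Study or Early Termination visit.) If there is none, use the last post-dose specimen before Day X. Do not carry baseline forward.
2. If there is no post-dose specimen, presume eradication only if the subject has no pneumonia signs or symptoms and no antibiotic with activity against the index strain at the assessment, over a stated look-back. The 48 hours in SAP Table 2 is one option; nothing at present ties it to eradication.
3. Otherwise, and for death before Day X, count as not eradicated. Without this, plain carry-forward would count a negative culture before death as eradicated.

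Under this rule, positive on Day 14 and negative on Day 24 gives not eradicated at Day 21 and, with no later specimen, eradicated at Day 28.

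Run the SAP 5.3 forward window as a sensitivity analysis, saying which specimen counts if several fall in it. Tabulate documented and presumed eradication separately. State how the committee's microbiological assessment is used.

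Protocol 9.3 leaves analysis details to the SAP, but eradication is defined in the protocol. Record the rule as a documented departure from the synopsis and Protocol 7.3, and from the closest-specimen text in Protocol 6.5 to 6.7.

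The cost is wording in three SAP sections, which SAP 1 says will be finalized before database lock, and a few extra tables. No new data are needed. The drawback is reliance on earlier specimens, some of them taken on antibiotics.
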